6.6 Supplementary/ Additional Analyses and Outcomes

In addition to the primary and secondary analyses, the following supplementary neuroimaging analyses will be conducted to provide further insight into the effects of digital CBT-I. These analyses focus on neuroimaging outcomes and their relationship with treatment response. Given their exploratory nature, results will be interpreted cautiously.

Magnetic Resonance Spectroscopy (MRS): Changes in neurotransmitter concentrations in the posterior insula at 3 months post-randomisation will be assessed using MRS. The primary focus will be on glutamate and γ -aminobutyric acid (GABA) levels, given their roles in pain processing and sleep regulation. Between-group differences will be examined using analysis of covariance (ANCOVA), adjusting for baseline neurotransmitter levels.

Resting-State Functional MRI (fMRI): Resting-state functional MRI will be used to examine changes in neuromarkers of sleep quality, pain, and sustained attention at 12 weeks. Functional connectivity within key attention-related networks, including the default mode network (DMN) and frontoparietal network (FPN), will be assessed. Treatment effects will be evaluated using whole-brain voxel-wise comparisons and seed-based connectivity analysis, adjusting for baseline connectivity measures.

Arterial Spin Labelling (ASL) Perfusion MRI: Changes in regional cerebral blood flow (rCBF) at 3 months will be assessed using ASL. Differences in perfusion within regions of interest associated with insomnia, pain, and

cognitive function (e.g., PAG, amygdala, anterior cingulate cortex, thalamus, and insula) will be examined. Group comparisons will be performed using voxel-wise and region-of-interest analyses, adjusting for baseline perfusion levels.

All neuroimaging analyses will be conducted on participants with usable baseline and follow-up scans, following established quality control procedures, using FSL tools. Sensitivity analyses will explore relationships between neuroimaging changes and clinical outcomes, such as FIQR improvement and changes in sleep parameters.

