9.2 Number of Participants

Previous work, using the ratio of tender to swollen joints as an indirect marker of central sensitization in patients with either RA or PSA, has shown that on average 43% of patients with low levels of likely central sensitization achieved remission (using DAS-28 remission criteria) compared to 23% in those with high levels of central sensitisation when being treated with either methotrexate or an anti-TNF agent. However a data simulation study showed that, for machine-learning methods, a sample size of 70 times the number of variables allows accurate identification of the data structure (36). Using the seven main variables of pain, fatigue, sleep disturbance, dyscognition, depression, anxiety and function, data for 490 participants, for each condition would be needed, including the feasibility study.

For the feasibility study 80 participants will be recruited in total, with 40 being assessed using MRI. Participants will be randomised on a 1:1 ratio to the intervention and standard care groups. This should provide a large enough sample to inform the practicalities of delivering dCBT-I, MRI assessments, and provide information on recruitment, uptake, and attrition, which will inform the design of the definitive trial. A moderate effect size (Cohen's d >0.3) would be sufficient to accept the result as worth investigating, in order to achieve a meaningful clinical benefit for patients, and in keeping with similar effects of CBT-I on cognitive outcomes in insomnia.

All participants in the Sleep sub-study will be invited to participate in the focus groups. However, it is envisioned that 18 (three groups of six participants) will take part, owing to the time commitment involved.

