3.2 Randomisation and Blinding

Patients will be randomised after consent and collection of baseline data. Participants will be randomised on a 1:1 basis using *Sealed Envelope*, a secure electronic randomisation platform. To ensure balanced group allocation, randomisation will be stratified by sex and completion of a brain MRI in the neuroimaging sub study, with participants assigned in blocks of 10. Outcome assessors will be blinded to treatment allocation for all study visits and communications with participants, and investigators carrying out analysis will also be blinded. Due to the nature of the intervention, participants were unable to be blinded.

To maintain allocation concealment, all study investigators will not have access to future group allocations and are unable to influence randomisation. The treatment allocation will be communicated to participants by an independent research nurse who is not involved in study visits or outcome assessments via email. This email will consist of scripted phrases and contained instructions for *Sleepio* access. In addition, the research nurse will act as an intermediary for any queries regarding the treatment or group allocation, and will relay questions regarding the intervention to the investigators anonymously to preserve blinding.

Due to the nature of the intervention, blinding participants was not possible. However, the outcome assessors will remain blinded to treatment allocation throughout the trial. Participants were instructed not to disclose their group assignment to study investigators during follow-up visits to maintain blinding. Participants cannot be blinded to their treatment. The outcome data will be collected directly from the participant. Outcome assessors will be blinded to the participant's treatment allocation.

Full details of the randomisation are available in se_list_242996464514928final, stored in the confidential statistical section of the TMF. No emergency randomisation plan was developed for this study.

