3.3 Sample Size

In the pilot phase (phase 1), the mean FIQR at baseline was 57.69 (SD=18.69). At the 3-month post-treatment follow-up, for the overall group, the mean FIQR was 52.24 (SD=19.06). The correlation between baseline and 3-month follow-up FIQR scores was high (r=0.86; 95%CI 0.73 to 0.93).

Using these values, the sample size was estimated to detect a minimum clinically-important difference (MCID) of 14% improvement in FIQR at 3 months (Bennett, Bushmakin, et al. 2009), corresponding to an improvement of 8.08 (Cohen's d=0.43) in this study, equating to a moderate effect size. Assuming a correlation of r=0.75 (the lower bound of the 95% CI for correlation), significance level of 0.05 and 80% power, the estimated sample size required to detect a 14% improvement in FIQR amongst participants in the Sleepio arm compared to the standard care arm using an ANCOVA is 78 participants (39 per group). This calculation includes an adjustment for a 3.33% loss-to-follow-up rate.

The R code used to estimate the sample size is provided below:

```

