3.7 Statistical Analysis Outline

It is anticipated that all the statistical analysis will be undertaken using R although other well-validated statistical packages, such as Stata, may be considered for statistical quality control validation analyses. All analyses will be carried out under a treatment policy strategy (that is, all participants will be analysed in the group they were randomised to regardless of actual treatment received).

The analyses will be repeated for the *per protocol* population (definition in section 4.2) as mandated by the protocol, bearing in mind that this may introduce bias by losing the benefits of randomisation and introducing ambiguity in the primary estimand of interest.

Although we have allowed for up to 5% missing data in the sample size at 3 months, we hope to minimise this by utilising data collection techniques appropriate to the fibromyalgia patient population. Before carrying out the within trial analysis, we will check the trial data for any missing data. Where possible the reasons for missing data will be ascertained and reported. The nature and pattern of the 'missingness' will be carefully considered — including whether data can be treated as missing at random (MAR). The handling missing data is detailed in section 6.3. Standard descriptive statistics will be used to describe the demographics between the treatment groups reporting means and standard deviations or medians and interquartile ranges as appropriate for continuous variables, and numbers and percentages for binary and categorical variables. All comparative outcomes will be presented as summary statistics and reported together with 95% confidence intervals and all tests will be carried out at a 5% two-sided significance level.

The Fibromyalgia Impact Questionnaire Revised (FIQR) at 3 months is the primary outcome of the study and the primary analysis will compare this between the treatment groups in a linear mixed effects method including all participant data, adjusting for the stratification factors.

Subgroups analyses will be undertaken with the aim of exploring the consistency of treatment effects across important baseline characteristics (Yusuf et al. 1991). These include:

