4. STATISTICAL PRINCIPLES

4.1 Statistical Significance and Multiple Testing

There is a single pre-specified primary outcome, so there is no correction for multiple testing. A significance level of 0.05 will be used, with 95% confidence intervals reported. All secondary analyses will be considered as supporting the primary analysis and will also be analysed using a significance level of 0.05 with 95% confidence intervals. No adjustment for multiple testing will be performed. In the setting of clinical trials, multiplicity adjustment is often inappropriate as it assumes all tested hypotheses are independent and equally relevant, which is rarely the case in this setting (for example, sleep quality, sleep efficiency, subjective dyscognition, and objective sustained attention are likely to be interrelated). Instead, adjustments like the Bonferroni correction can overcorrect, reducing statistical power and potentially obscuring meaningful clinical findings, especially when endpoints are interrelated and when clinical interpretation is more relevant than strict statistical significance(Schulz and Grimes 2005).

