6.2 Analysis Methods

Analysis of Primary Estimand (ATE): A Treatment Policy Analysis

Unadjusted summary statistics of the FIQR scores will be displayed by treatment allocation using means and standard deviations at each assessment point. The primary analysis will be conducted using **Constrained Longitudinal Data Analysis (cLDA)**(Lu 2010). This model includes baseline FIQR as part of the response vector while constraining baseline means to be identical across treatment groups, ensuring that differences in FIQR post-randomisation reflect true treatment effects rather than baseline imbalance. This method offers advantages over traditional mixed-effects models (LMM) and ANCOVA by providing a more efficient and unbiased estimate of treatment effects while maintaining the interpretability of a baseline-adjusted analysis(Coffman, Edelman, and Woolson 2016; Lu 2010).

A linear mixed-effects model (LMM) with constraints will be used to compare FIQR scores between treatment groups across all available time points (baseline, 3-months, 6-months, and 12-months), ensuring that baseline differences are accounted for without requiring explicit adjustment in the fixed effects. The model will include a fixed effect for treatment group, time (categorical), and their interaction to allow for non-parallel treatment effects over time. To account for repeated measures within individuals, a random intercept will be specified for each participant, and an unstructured covariance structure will be assumed for residual errors to allow for flexible correlation between repeated measurements.

The constrained longitudinal model will be specified as:

$$Y_{i,t} = \mu + \gamma_t Time_t + \delta_t (Treatment_i \times Time_t) + \sum_k \beta_k Covariate_{k,i} + u_i + \varepsilon_{i,t}$$

where:

- *Y_{i,t}* is the FIQR score for participant *i* at time *t*
- μ is the grand mean FIQR score at baseline, constrained to be equal for both treatment groups
- $\gamma_t Time_t$ is the fixed effect of time (categorical), with baseline as the reference category
- δ_t is the interaction effect between treatment and time, estimating the treatment effect at each follow-up time point
- β_k represents covariate adjustment terms for stratification factors (sex, participation in the MRI substudy)
- $u_i \sim N(0, \sigma_u^2)$ represents the random intercept for participant i
- $\varepsilon_{i,t} \sim N(0, \sigma_t^2)$ is the residual error term

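### The imaging comparisons in SAP 6.6 leave out sex, the one randomisation stratum that still varies within the MRI sub-study

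*SAP*

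**What the plan says.** SAP 6.6 sets out three supplementary imaging comparisons, which it calls exploratory, and limits all of them to one analysis set: "All neuroimaging analyses will be conducted on participants with usable baseline and follow-up scans". For glutamate and GABA the model is explicit: "Between-group differences will be examined using analysis of covariance (ANCOVA), adjusting for baseline neurotransmitter levels". For resting-state connectivity and regional blood flow, the only adjustment named is the baseline measure.

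SAP 3.2 says that "randomisation will be stratified by sex and completion of a brain MRI in the neuroimaging sub study". SAP 3.7 adjusts the primary analysis for the stratification factors. The model in SAP 6.2 includes sex and MRI sub-study participation as covariates, and 6.2 extends the same methods to a list of secondary outcomes. That list includes actigraphy and objective cognition, which, like MRI, are measured only at baseline and 3 months. Imaging is not on it.

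SAP 6.2 also says of its constrained longitudinal model (cLDA): "This method offers advantages over traditional mixed-effects models (LMM) and ANCOVA by providing a more efficient and unbiased estimate of treatment effects". The size of the MRI sub-study is given only in Protocol 9.2: 80 recruited, "with 40 being assessed using MRI".

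**The concern.** The trial randomises by sex, so the arms should be close to balanced on sex within the MRI sub-study. A model without sex ignores that balance. Variation due to sex stays in the residual, although the design has largely removed it from the arm difference. The standard error then overstates the true uncertainty, intervals are too wide and tests are conservative.

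These comparisons address how the intervention might work, with about 20 participants per arm at most, so avoidable width matters. The SAP already makes this adjustment for its other outcomes and gives no reason for leaving it out here.

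**Working it through.** **Inputs from the documents.** 40 MRI participants (Protocol 9.2), taken as 20 per arm under 1:1 allocation. Two scans, at baseline and 3 months (SAP 6.1). Two-sided 5% tests (SAP 3.7: "all tests will be carried out at a 5% two-sided significance level").

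**Assumed, because the documents give nothing for imaging.** The share of residual variance explained by sex (R²), the number of men, the baseline to follow-up correlation r, and the rate of unusable scans.

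**The plan's own figure.** No power or precision is stated for imaging. The only calculated sample size is for FIQR (SAP 3.3, "significance level of 0.05 and 80% power"). It reproduces: 85 × (1 − 0.75²) = 37.19 per arm; 37.19 / (1 − 0.033), rounded up, is 39 per arm, 78 in total. It does not bear on the imaging analyses.

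**1. Standard error without sex, sex exactly balanced between arms.** The ANCOVA has three fitted parameters (intercept, arm, baseline), so the sex variation enters a residual with N − 3 degrees of freedom. Reported SE divided by true SE is about √[1 + N/(N − 3) × R²/(1 − R²)]. With N = 40, N/(N − 3) = 1.081:

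| R² | Calculation | SE ratio |
|---|---|---|
| 0.05 | √(1 + 1.081 × 0.0526) | 1.028 |
| 0.10 | √(1 + 1.081 × 0.1111) | 1.058 |
| 0.20 | √(1 + 1.081 × 0.2500) | 1.127 |

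A simulation with exactly balanced allocation, 40 participants and either 4 or 10 men agrees. Without sex the reported SE was about 3%, 6% and 12–13% too large, and the type I error of a nominal 5% test fell to about 2.6–2.7% at R² = 0.20. With sex in the model the SE was correct. When sex was irrelevant, adding it cost essentially nothing.

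**2. Cost of adding sex when balance is not guaranteed.** Blocks of 10 and few men may leave a block unfilled, and unusable scans can disturb the balance. The conservative case treats sex as an ordinary covariate, with variance factor (1 − R²)(N − 5)/(N − 6). At N = 40 and R² = 0 this is 35/34 = 1.029, so the SE rises by a factor of √1.029 = 1.015. Break-even is R² = 1/35 = 0.029. At R² = 0.05 the SE ratio is 0.989, and at 0.10 it is 0.963. If only 32 pairs remain, the worst case is √(27/26) = 1.019.

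**3. Would cLDA recover precision?** On complete pairs the ANCOVA variance, in SD² units, is 2(1 − r²)/(pairs per arm). This is compared with generalised least squares for two visits with a common baseline mean, 20 per arm, r = 0.5:

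| Pattern per arm | ANCOVA variance | cLDA variance | SE ratio |
|---|---|---|---|
| 20 pairs | 0.0750 | 0.0750 | 1.000 |
| 18 pairs, 2 baseline only | 0.0833 | 0.0833 | 1.000 |
| 18 pairs, 2 follow-up only | 0.0833 | 0.0769 | 0.961 |
| 16 pairs, 4 follow-up only | 0.0938 | 0.0789 | 0.918 |

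All the gain comes from participants with a usable follow-up scan and an unusable baseline scan. The documents do not say how many there will be. If the FIQR loss rate of 3.33% applied to scans at each visit, there would be about 20 × 0.0333 × 0.9667 = 0.64 such participants per arm. The SE would then fall by 0.9–1.5% for r between 0.7 and 0.3.

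**The case against.** The strongest reply is that nothing here is contradictory or invalid. The stratum adjustment in SAP 3.7 and 6.2 is written for the primary and listed secondary outcomes, and imaging is not among them. ANCOVA on the baseline value is a standard, valid analysis. The imaging work is labelled exploratory and is to be interpreted cautiously. The effect of sex on these measures is unknown, and SAP 3.1 itself notes the sex imbalance in fibromyalgia, so there may be very few men among 40.

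Most of this stands. It makes the point small and rules out calling the omission a breach of the SAP's own rule. It does not supply a reason for leaving sex out: the factor was used to randomise, and the cost of including it is negligible.

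A reader might also infer a stronger point: because SAP 6.2 calls cLDA more efficient than ANCOVA, the complete-pair rule must cost the sub-study precision. The documents do not support this. With one follow-up scan, the two methods give the same precision when only follow-up scans are missing, which is how ordinary attrition appears. The gain depends entirely on a baseline scan-failure rate that is not stated.

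Nor could the 6.2 model be copied across as worded. A random intercept plus an unstructured residual covariance is over-parameterised for two visits, and no small-sample method is named. In a simulation (20 per arm, r = 0.5, 10–20% of scans unusable, 1,500 trials per setting), maximum-likelihood cLDA with Wald tests had a type I error of 8–9%, against about 5.7% for ANCOVA.

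**Conclusion.** The point holds in a limited form. SAP 6.6 leaves out the one stratification factor that varies within the MRI sub-study, while the SAP adjusts its primary and listed secondary outcomes for such factors. If sex predicts an imaging outcome, the reported standard errors are too large, by about 3% at R² = 0.05 and 6% at R² = 0.10. These figures assume 40 participants with both scans usable and arms balanced on sex; the R² values are assumptions. If sex explains nothing, the omission does no harm.

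The consequence is conservative inference. No bias is shown in the estimated arm difference, and no general loss of precision from using ANCOVA or complete pairs should be claimed. As the analyses are exploratory, this is a minor correction that is cheap enough to make.

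**What to change.** In SAP 6.6, add sex as a covariate to the spectroscopy ANCOVA, to the region-of-interest perfusion and seed-connectivity models, and to the voxel-wise design matrices. MRI participation needs no term, because it is constant in this sub-study. The cost is one sentence in the SAP and one degree of freedom: at most about 1.5% in SE with 40 participants, and close to nothing if the arms are balanced on sex.

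Optionally, for scalar imaging outcomes only, add a sensitivity analysis that brings in participants with a usable follow-up scan but an unusable baseline scan. This would be a two-visit model with a common baseline mean, an unstructured covariance and no extra random intercept, fitted by REML with a small-sample degrees-of-freedom correction. It assumes that unusable scans are missing at random. It need be run only if such participants exist.

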6.7 Harms

This is a low risk, pragmatic trial where the intervention, dCBT-I, is in common use. Thus, we do not anticipate many SAEs. All adverse events are submitted to the trial investigators only if they arise within 12 months post-randomisation and they fall under the category of an SAE: events resulting in death; life-threatening; required hospitalisation; prolonged hospitalisation; other important medical event which may require medical or surgical intervention to prevent one of the serious outcomes listed. SAEs potentially related and unexpected are recorded on the trial's database and assessed for seriousness, causality and expectedness (**Table 6**).

Table 6. List of serious adverse events

Allocatio n	Diagnosi s	Timin g of inset of event ¹	Descriptio n of event (including signs & symptoms)	Action taken to deal with the event (including an treatments)	Reason for seriousness 2	Causality: is the event related to the intervention? ³	Expectednes s (in relation to what is known about the intervention) 4

¹ post-randomisation weeks

² Death; Life-threatening; required hospitalisation; prolonged hospitalisation; other important medical event which may require medical or surgical intervention to prevent one of the serious outcomes listed. ³ Possibly related; Probably related; Definitely related

⁴ Expected; Unexpected

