8 SAFETY REPORTING

8.1 Definition of Serious Adverse Events

A serious adverse event is any untoward medical occurrence that:

- · results in death
- is life-threatening
- requires inpatient hospitalisation or prolongation of existing hospitalisation

- results in persistent or significant disability/incapacity
- consists of a congenital anomaly or birth defect.

Other 'important medical events' may also be considered serious if they jeopardise the participant or require an intervention to prevent one of the above consequences.

NOTE: The term "life-threatening" in the definition of "serious" refers to an event in which the participant was at risk of death at the time of the event; it does not refer to an event which hypothetically might have caused death if it were more severe.

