Magnetic Resonance Imaging (MRI): A neuroimaging sub-study will be nested within the trial, with eligible participants invited to also undergo a brain MRI at the baseline (pre-randomisation) and 3-month study visits. Neuroimaging data will be acquired on a 3T Siemens Prisma MRI scanner at the Oxford Centre for Functional MRI of the Brain (FMRIB) at the John Radcliffe Hospital in Oxford. Participants will complete whole brain structural, resting state BOLD imaging, ASL imaging, and H1-MRS of the posterior insula.

Complications: Adverse events will be measured pre-randomisation (baseline), and at 3-, and 6-months via the REDCap electronic survey tool. Participants will be asked to report any potential adverse events related to dCBT-I, including physical and psychological symptoms such as fatigue, low mood, pain, and difficulty concentrating. The will rated the severity of these symptoms and how much they interfere with normal functioning, on a scale from "Did not experience" to "Very much." Participants will also report incidents of sleepiness over the preceding 3 months, including hospital admissions, accidents, falls, or near-miss incidents, and have the opportunity to mention any other relevant events.

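### SAP 6.7 filters SAEs on relatedness and expectedness before recording them, narrows the protocol's SAE definition, and gives the solicited adverse events no by-arm table

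*SAP*

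**What the plan says.** **SAEs.** SAP 6.7 (Harms) first sets what reaches the investigators: "All adverse events are submitted to the trial investigators only if they arise within 12 months post-randomisation" and they meet the definition of serious. The criteria are "events resulting in death; life-threatening; required hospitalisation; prolonged hospitalisation; other important medical event which may require medical or surgical intervention" (that is, to avert one of the other outcomes). It then sets what is kept: "SAEs potentially related and unexpected are recorded on" the database, where seriousness, causality and expectedness are then assessed. Table 6 lists the recorded events with a column for allocation. Its causality column asks about relation to the intervention and offers three grades, all of them related (possible, probable, definite). Its expectedness column offers expected or unexpected.

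**Protocol.** Section 8.1 has further criteria, including an event that "results in persistent or significant disability/incapacity" and congenital anomaly. It also counts as serious an important medical event that jeopardises the participant. Section 8.2 uses related and unexpected as the test for reporting an SAE to the ethics committee.

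**Solicited events.** SAP 6.1 lists Complications under its secondary outcomes. "Adverse events will be measured pre-randomisation (baseline), and at 3-, and 6-months" by online survey. On content, the SAP says: "Participants will be asked to report any potential adverse events related to dCBT-I, including physical and psychological symptoms such as fatigue, low mood, pain". Trouble concentrating is also named, and each symptom has a severity rating. The survey also asks about sleepiness-related admissions, accidents, falls and near misses.

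**The concern.** An SAE should enter the data because it happened. Whether it was related or expected is a classification made afterwards. SAP 6.7 reverses this order, so the database can hold only events that someone already thought might be due to treatment and had not anticipated. Relatedness is far easier to suspect where a participant has received an active programme than where the participant has received sleep hygiene advice alone. A listing selected in this way can show an imbalance that does not exist, or show nothing when SAEs did occur.

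The narrower definition adds a second filter. Some events that are serious under the protocol would not count under the SAP.

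The solicited survey is the one source that asks trial participants the same questions at fixed times, and it is not restricted to one arm. Its use in the analysis is left to a general sentence. SAP 3.4 provides for no data monitoring committee and no interim analysis, so the final harms section carries most of the trial's safety reporting. SAP 6.3 also draws on the 6.7 SAEs when it examines predictors of drop-out.

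**Working it through.** **1. Arm size.** The documents give no numerical target for harms, so the only relevant figure is the sample size in SAP 3.3.
- Difference: 0.14 × 57.694 = 8.077. Effect size: 8.077 / 18.688 = 0.432.
- Per group before adjustment: 2 × (1.960 + 0.842)² / 0.432², rounded up = 85.
- With r = 0.75: 85 × (1 − 0.75²) = 37.19.
- With 3.3% loss: 37.19 / 0.967 = 38.5, rounded up to 39. The total is 78, as the SAP states.

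**2. The recording rule against Table 6 and protocol 8.2.**
- Entry requires potential relatedness. Table 6 then cannot return an unrelated verdict, so the later causality assessment can only grade relatedness.
- Entry requires unexpectedness. Table 6 nevertheless allows an expected event. Rule and table cannot both be applied as written.
- Protocol 8.2 applies the same two conditions to onward reporting to the ethics committee, and says nothing about limiting what is recorded. The SAP has made a reporting test into a recording rule.

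**3. Seriousness criteria.**

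| Criterion | Protocol 8.1 | SAP 6.7 and Table 6 footnote |
|---|---|---|
| Death | yes | yes |
| Life-threatening | yes | yes |
| Hospitalisation, new or prolonged | yes | yes |
| Disability or incapacity | yes | no |
| Congenital anomaly or birth defect | yes | no |
| Important medical event: jeopardises the participant | yes | no |
| Important medical event: needs intervention | yes | yes |

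**4. What the filter could do.** The documents give neither an SAE risk nor the share of events that would pass the filter. All rates here are assumptions, chosen only to show direction and scale. Expected recorded events = 39 × true SAE risk × share passing. The true risk is set equal in both arms.

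| True risk, both arms | Share passing, dCBT-I / control | Recorded, dCBT-I | Recorded, control |
|---|---|---|---|
| 10% | 100% / 100% (no filter) | 3.90 | 3.90 |
| 10% | 50% / 5% | 1.95 | 0.20 |
| 10% | 20% / 0% | 0.78 | 0.00 |
| 5% | 100% / 100% (no filter) | 1.95 | 1.95 |
| 5% | 50% / 5% | 0.98 | 0.10 |
| 5% | 20% / 0% | 0.39 | 0.00 |

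With no true difference, the filtered listing leans towards dCBT-I. Most events are lost: with equal arms, 1 − (0.50 + 0.05)/2 = 72.5% in the first scenario and 1 − (0.20 + 0)/2 = 90% in the second, whatever the true risk. The allocation column in Table 6 cannot correct for events that were never entered.

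**5. Tracing the solicited events through the SAP.**
- 6.1: collected at baseline, 3 and 6 months, under secondary outcomes.
- 3.7: secondary clinical outcomes get mixed-effects logistic or linear regression, and comparative outcomes get summary statistics with 95% confidence intervals. This can reach the solicited events, but it does not say which item is the endpoint or how the graded severity scale is to be coded.
- 6.2: the named list of secondary outcomes covers cognition, sleep and pain, and leaves Complications out. It also says that its outcomes run to 12 months except actigraphy and objective cognition; the solicited events stop at 6 months, so they do not fit that description.
- 6.7: the solicited events are not mentioned, and the only table is the SAE listing.

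**The case against.** The best defence is that the recording sentence is loose wording carried over from the ethics-committee rule in protocol 8.2. It says potentially related, formal causality comes later, and the expected code in Table 6 would be redundant if the filter were really applied. SAEs of any cause within 12 months are submitted to the investigators, so they need not be lost. This shows that the text may not reflect practice. It does not rescue the text, which contradicts itself and, if followed, keeps unrelated SAEs off the database.

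It can also be said that the definition gap is small. Pregnancy is an exclusion, so congenital anomaly has little practical weight. That is fair; disability and the jeopardy limb remain. The symptom items also overlap with outcomes that are compared by arm: the FIQR covers pain, fatigue and mood, the BC-CCI concentration and the SF-36 bodily pain. That is fair too, but the sleepiness incidents have no such counterpart.

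Four stronger readings are tempting, and the documents do not support them.
- *An unblinded person decides relatedness.* SAP 3.2 leaves only participants unblinded; outcome assessors and analysing investigators are blinded. Neither document says that relatedness is judged with knowledge of allocation.
- *The SAP never compares solicited harms, or harms cannot be compared at all.* The rule in 3.7 can reach them, the survey is not limited to one arm, and Table 6 shows allocation.
- *After 6 months SAEs are found only by spontaneous report.* The adverse-event survey does stop then, but nothing makes it the route for detecting SAEs. Protocol 7.5 schedules a medical-history update at 50–54 weeks after the start of treatment in the parent cohort, and SAP 3.5 sends 12-month data to a separate plan.
- *The precision available from 39 per arm measures the fault.* It would be the same with perfect recording.

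**Conclusion.** The point holds in a limited form. As written, SAP 6.7 selects SAEs on potential relatedness and unexpectedness before recording them, its coding contradicts that selection, and its definition of serious is narrower than protocol 8.1. Under that rule the recorded SAEs do not support an unbiased comparison by arm. The solicited events could be compared, but no endpoint, coding or table is specified for them.

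This conclusion assumes that relatedness in the recording sentence means relatedness to the intervention, as in Table 6's causality column, and that dCBT-I is what distinguishes the arms. If relatedness to research procedures common to both arms were meant, as in protocol 8.2, the filter would be less lopsided but would still drop unrelated SAEs. The size cannot be fixed from the documents; the counts above are illustrations. Few SAEs are anticipated, so even full recording would give a descriptive comparison. The primary FIQR analysis is not affected. The text should nevertheless be corrected, because a report of no SAEs under the present wording could reflect the entry rule as much as the treatment.

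**What to change.** In SAP 6.7:
1. Record, list and count by arm every SAE submitted to the investigators, whatever its relatedness or expectedness, using the protocol 8.1 definition in full in both the text and the Table 6 footnote.
2. Classify causality and expectedness after entry, and add a 'not related' code to Table 6. Keep related-and-unexpected solely as the test for reporting to the ethics committee.
3. Add a table of counts and percentages by arm, at 3 and 6 months, for the solicited symptoms and sleepiness incidents in SAP 6.1, and state how the severity scale is coded. Add a cross-reference from 6.2 so that the analysis does not rest on the general sentence in 3.7.

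The cost is a wording change, one extra table from data already planned for collection, and a small amount of extra SAE data entry. If SAEs have so far been entered only when they passed the filter, the others would have to be retrieved from the reports sent to the investigators.
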